Study Protocol

Official Title: Adapting acceptance and mindfulness-based behavior therapy for aphasia

ClinicalTrials.gov ID (NCT number): NCT04984239

Protocol Date: 11/4/2020

Scientific Background

Post-stroke aphasia has profound and lasting negative effects on health-related quality of life at levels greater than cancer, Alzheimer's disease, or Amyotrophic Lateral Sclerosis. Aphasia is a language disorder caused by acquired brain injury that affects 30-40% of stroke survivors and more than 2.5 million people in the United States. For stroke survivors with aphasia, their psychosocial responses to the sudden and unexpected loss of language promote or inhibit their ability to adapt, adjust, and recover after stroke.

To a large extent, practicing rehabilitation professionals are currently unprepared to address the relationship between psychosocial adjustment and aphasia rehabilitation. Traditional evidence-based language interventions fail to address psychosocial factors, and speech-language pathologists report feeling unprepared to address counseling needs during aphasia rehabilitation. In addition, mental health professionals report feeling unprepared to work with people with aphasia. Ultimately, workforce training based on effective behavioral interventions is required to address the specific unmet needs of this vulnerable and underserved population. The first step in this endeavor is to develop and pilot integrated interventions that simultaneously address the counseling and communication needs of stroke survivors with aphasia.

The current Stage I project seeks to develop a new intervention will that integrate language compensation training and Acceptance and Commitment Therapy (ACT). ACT is a behavioral intervention designed to improve psychological flexibility, allowing people to take action consistent with their values, even in the presence of persistent emotional distress. Psychological flexibility predicts quality of life and mental health in a variety of populations. In small-scale efficacy studies, ACT has improved psychological flexibility in stroke survivors, and has resulted in large effect sizes when combined with compensatory training in people who stutter. Yet, no prior work has adapted ACT to meet the specific needs of people with aphasia, excluding a large and vulnerable subset of stroke survivors from accessing an effective intervention.

ACT is an ideal match for stroke survivors with aphasia and integrating language compensation training and ACT is more than the sum of its parts. ACT will only be fully accessible to people with aphasia if modified to include communication supports. In addition, language compensation training works by training alternative communication techniques (e.g., writing, gesturing, self-cueing) to maximize functional communication. However, stroke survivors with aphasia must demonstrate psychological flexibility for such training to be effective. They must reconceptualize what it means to communicate and overcome potential fears of how they will be perceived. They must become comfortable using communication techniques in distressing situations they would rather avoid (e.g., communicating with unfamiliar and rude store employees). ACT improves psychological flexibly via approaches such as teaching clients to develop a more flexible response repertoire when pursuing valued life directions and mindfully gaining distance from self-critical thoughts. Improving communication skills and psychological flexibility together will simultaneously address the unmet communication and psychosocial needs of stroke survivors with aphasia.

Study Objectives

Objective: To develop and pilot an "ACT for Aphasia" treatment manual designed to improve communication participation, psychosocial adjustment, and quality of life for stroke survivors with aphasia.

Aim 1: Collaborate with a Stakeholder Advisory Board (SAB) to develop and refine an ACT for Aphasia treatment manual via an iterative design process.

We will work with a SAB of stroke survivors with aphasia and caregivers to develop an initial version of the manual, then refine it using a successive cohort design. The first cohort will consist of 5 participants with aphasia, who will be interviewed after treatment completion. A second cohort (N=16) will complete the revised intervention and provide feedback via interviews to

inform a second manual revision. This will result in a comprehensive, iteratively refined, stakeholder-driven treatment manual.

Aim 2: Establish intervention feasibility and acceptability

Feasibility will be assessed through intervention adherence, recruitment, participation, and completion rates. Acceptability will be assessed using the Client Satisfaction Questionnaire – 8 post-treatment; ACT for aphasia will be considered acceptable if the group mean is \geq 28 for the second cohort. As a secondary aim, preliminary effect sizes will also be estimated on pre-post measures of successful communication participation, psychological distress, and quality of life, along with point estimates and standard deviations to inform power analyses for a Stage II efficacy trial.

Study Design & Methods

Participant assignment: given the early phase of this research and the lack of control conditions or groups, there will be no random assignment. Participants will be enrolled in the study as they are referred and found to be eligible, with the first five participants being enrolled in the first study cohort during year 1 while the remainder of participants will be enrolled in the second cohort across years 1 and 2.

Screening procedures:

We will partially assess eligibility prior to informed consent, and finalize screening for eligibility after informed consent via interview and standardized assessments.

Pre-treatment assessments:

Participants will be assessed with a primary outcome measure (the Client Satisfaction Questionnaire-8) and several secondary outcome measures (screening questions, the Communication Participation Item Bank, the Aphasia Communication Outcome Measure-ACOM, the Stroke and Aphasia Quality of Life, the Acceptance and Action Questionnaire – ABI, the Kessler K6 non-specific distress scale, the Acceptance and Action Questionnaire II, the Modified University of Washington Resilience Scale (added for the second study cohort only), and the Comprehensive aphasia test).

Intervention description: the ACT for Aphasia treatment manual will be a 10-session intervention created by modifying an existing ACT manual provided by [name]. To meet the specific needs of stroke survivors with aphasia, ACT will be modified in two main ways.

First, the intervention will include modified language and communication supports to address the unique communication challenges faced by people with aphasia that could impede engagement with ACT content. Multi-modality communication supports will be provided by the treating clinician (e.g., writing out key words to support verbal content, summarizing and providing repetitions, providing session summaries to review between sessions). Manual creation will follow existing practice recommendations for modifying counseling interventions for PWA (e.g., simplifying language and increasing use of visual metaphors) which will be reviewed by the SAB.

Second, ACT will be further augmented via individualized language compensation training and a focus on identifying and addressing communication-based barriers to life participation. Language training will focus on active compensatory strategies such as self-cuing, use of alternative modalities (gesture, writing), and use of commonly available technology (e.g., smartphone dictionaries, text-to-speech). The details of this language compensation training will also be determined based on input from the Stakeholder Advisory Board (SAB), and will be revised after reviewing performance and interview feedback from each successive cohort.

Post-treatment phase:

In this phase, participants will be given the same series of assessments received in the pre-treatment phase. In addition, they will have an interview to provide feedback about the intervention and suggestions for improvement.

Post-treatment interviews providing feedback for protocol revision will be administered by trained study staff within three weeks of treatment completion.

Interviews will use a semi-structured, ethnographic interview approach and be video-recorded. These interviews will ask specific questions about the participant's experience and perspective regarding each functional domain of the intervention (i.e., the "Open Up," "Be Present," and "Do What Matters" components of ACT and the individualized language compensation training), and will be asked for suggestions and improvements about the specific content and techniques employed.

Eligibility Criteria

Inclusion Criteria:

Participants will be age 18 or older with an existing diagnosis of aphasia subsequent to left hemisphere stroke as confirmed by a) registry referral sources or b) personal copies of medical records (provided by the participant following informed consent).

Exclusion Criteria:

Exclusionary criteria at enrollment include a history of other acquired or progressive neurological disease, significant language comprehension impairments, significant semantic memory impairments, unmanaged drug /alcohol dependence, and severe diagnosed mood or behavioral disorders that require specialized mental health interventions.

Participants with severe language comprehension impairments will be excluded, as the intervention relies on a base level of comprehension to understand instructions and counseling content. Therefore, participants will be excluded if their spoken language comprehension mean modality T-score on Comprehensive Aphasia Test falls below 40. Furthermore, we will exclude participants with semantic memory deficits (8/10) on the Comprehensive Aphasia Test. We will also exclude participants with active drug/alcohol dependence and progressive neurological disease such as dementia or primary progressive aphasia, as these comorbid factors could affect treatment response and require alternative specialized interventions.

Sample Size Justification

Given the pilot nature of this study, sample size was chosen to determine acceptability and feasibility of our novel intervention without a formal power analysis.

Total sample size (N=21; N=5 for Cohort 1 and N=16 for Cohort 2) is considered to be realistic based on level of project staffing and previous experience recruiting PWA in the Pittsburgh area.

The sample size for Cohort 1 was chosen to provide preliminary feedback for the first version of the treatment manual.

The sample size for Cohort 2 is considered adequate for providing a precise estimate of treatment acceptability. This is because even with an overly conservative attrition rate of 25%, final completion rates would still be N=12, which meets minimum recommendations for providing reasonably precise confidence intervals for continuous variables (Julious, 2005)

Julious SA. Sample size of 12 per group rule of thumb for a pilot study. Pharm Stat. 2005;4(4):287-291. doi:10.1002/pst.185.

## 4.4. Statistical Design and Power.

The purpose of this overall research agenda is to improve communication participation, psychosocial adjustment, and quality of life (QoL) for stroke survivors with aphasia by developing an effective new integrated language and counseling, *Act for Aphasia*. At this preliminary research stage, our primary goals are to develop and pilot this intervention, laying the groundwork for a subsequent larger-scale efficacy trial. Therefore, in **Aim 1**, we will engage a stakeholder advisory board to develop and revise the treatment manual. In **Aim 2a** we will establish primary outcomes of **acceptability** and **feasibility** of ACT for Aphasia. In **Aim 2b** we will estimate preliminary effect sizes on secondary outcome measures to inform power analyses for a subsequent randomized control trial.

Methods for Determining Intervention Acceptability. Acceptability will be assessed using the Client Satisfaction Questionnaire − 8. It consists of 8 questions rated on a 4-point scale (summed scores range from 8 to 32). Participants will be given these questions at the end of follow-up assessment with an independent assessor. High scores indicate high satisfaction. We will consider *Act for Aphasia* to be acceptable if the group mean ≥28, a benchmark based on previous stroke rehabilitation work by project consultant [name].

**Methods for Determining Intervention Feasibility.** Feasibility will be assessed by examining intervention adherence (the number of treatment sessions successfully completed), recruitment and participation rate (the number of eligible PWA identified and the percentage of PWA who choose to enroll), and completion rate (the percentage of enrolled participants who complete the follow-up assessment). The intervention will be considered to demonstrate adequate adherence if participants if participants complete at least 75% of weekly treatment sessions within a 12-week period. We will not pre-determine cutoffs for other measures of intervention feasibility (recruitment, participation, and completion rate), but will take them into careful consideration when considering protocol modifications and study design considerations for the next phase of this research. For example, required sample size estimates for an efficacy trial will be compared against recruitment and participation rates to determine whether data collection could be successfully completed at a single Pittsburgh site, or require multiple sites. If multi-site research was required, it could take advantage of the University of Pittsburgh's status as a NIH Clinical and Translational Science Award Program Hub in the Trial Innovation Network, dedicated to supporting multi-center clinical trial research.

**Initial estimates of treatment effects.** We will assess change on two types of secondary outcome measures, ones that measure mechanisms of treatment action, and ones that measure functional outcomes. Assessments that measures mechanisms of treatment action will consist of the Acceptance and Action Questionnaire II,  which measures general psychological flexibility, the Acceptance and Action Questionnaire – ABI,  which measures psychological flexibility in relation to acquired brain injury, and the Values Tracker,  which measures values engagement. Functional outcome measures will consist of the K6,  which measures psychological distress, the Stroke and Aphasia Quality of Life – 39,  which measures QoL, the Aphasia Communication Outcome Measure,  which measures self-reported communication efficacy, and the Communication Participation Item Bank,  which measures communication participation. For these measures, we will calculate pre- to post-treatment changes by calculating standard effect sizes (Cohen's *a*). These functional outcome measures will serve as primary outcome measures in planned Stage II efficacy research, should ACT for aphasia appear promising (see "Use of pilot data to inform development of a full-scale efficacy trial" below).

**Statistical Approach.** Primary outcomes will assess intervention feasibility and acceptability. Secondary outcome measures will provide initial estimates of participate response and variability. We will report means and standard deviations for continuous variables and frequencies and proportions for categorical variables, with 95% confidence intervals for both types of variables. As a preliminary check on treatment validity, we will explore the association between changes on mechanistic measures (i.e., psychological flexibility, values engagement) and secondary measures of functional outcomes (e.g., QoL) via multi-level regression models (please see Clinical Trials Information Section 4.4 for additional information). We will also examine whether biological sex exerts an effect on any primary acceptability and feasibility outcomes measures via appropriate statistical tests (e.g., a two-sample *t* test or nonparametric alternatives, depending on data distributions).

**Sample size justification.** Total sample size (N=21; N=5 for Cohort 1 and N=16 for Cohort 2) is considered to be realistic based on level of project staffing and previous experience recruiting PWA in the Pittsburgh area. The sample size for Cohort 1 was chosen to provide preliminary feedback for the first version of the treatment manual, while also making sure the size of the SAB stays manageable over time (should all five participants decide to join the SAB when invited, this would bring the total number of SAB members to nine). The sample size for Cohort 2 is considered adequate for providing a precise estimate of treatment acceptability. This is because even with an overly conservative attrition rate of 25%, final completion rates would still be N=12, which meets minimum recommendations for providing reasonably precise confidence intervals for continuous variables.

Use of pilot data to inform development of a full-scale efficacy trial. The determination of whether a full-scale trial is warranted will be based on whether ACT for Aphasia meets our criteria for feasibility and acceptability (Aim 2a) and whether it appears to be promising in terms of promoting functional recovery (Aim 2b). We will also examine within-group effect sizes (with 95% confidence intervals to reflect uncertainty regarding the reliability of the treatment effects sizes for planning a subsequent trial). Should ACT for Aphasia appear promising, these data will be used to inform the power analysis to determine sample size for a subsequent efficacy trial.

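### Does the SAP's acceptability rule leave open whether Cohort 1 scores count towards the mean of 28?

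*SAP*

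**What the plan says.** The rule appears twice. In SAP section 4.4, under the methods for determining acceptability, the intervention is considered "to be acceptable if the group mean ≥28, a benchmark based on previous stroke rehabilitation work". No cohort is named. In the protocol, Aim 2 gives the same threshold with its population attached: "28 for the second cohort. As a secondary aim, preliminary effect sizes will also be estimated on pre-post measures".

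The cohorts have different purposes. Under the protocol's Aim 1, "A second cohort (N=16) will complete the revised intervention and provide feedback via interviews", whereas the first five participants are treated with the initial manual. The SAP's sample size justification says "The sample size for Cohort 1 was chosen to provide preliminary feedback for the first version of the treatment manual" and, separately, "The sample size for Cohort 2 is considered adequate for providing a precise estimate of treatment acceptability".

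Cohort 1 should also have satisfaction scores. The protocol's assessment list restricts one instrument by cohort, "the Modified University of Washington Resilience Scale (added for the second study cohort only", and after treatment "participants will be given the same series of assessments received in the pre-treatment phase". The SAP's statistical approach plans means and standard deviations "with 95% confidence intervals for both types of variables".

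**The concern.** Acceptability is a primary outcome, the cut-off of 28 is its only criterion, and meeting it is one of the inputs to the decision on a full-scale trial. A rule of that kind should say whose scores enter the mean. Read alone, the SAP sentence could cover all 21 participants, and that mean could be computed because Cohort 1 completes the questionnaire too.

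The cohorts are not interchangeable, since the manual is revised between them. If the revision works as intended, Cohort 1 would tend to score lower and pooling would count against the final version. If Cohort 1 happened to be unusually satisfied, pooling could carry a failing Cohort 2 over the line. On that reading the protocol and the SAP could give different verdicts on the same data.

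**Working it through.** **Inputs.** From the documents: cohort sizes 5 and 16; 25% attrition; threshold 28; scale range 8 to 32. Assumed, because the documents give neither: the SD of the score (2 to 5) and the true cohort means.

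**The plan's own figure.** 16 × (1 − 0.25) = 12 completers in Cohort 2, and 5 + 16 = 21 in total. Both agree with the documents. There is no power calculation to reproduce.

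**Which cohort do the documents point to?**

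| Place | What it implies |
|---|---|
| Protocol, Aim 2 | Threshold applies to Cohort 2 |
| SAP 4.4, acceptability methods | Threshold applies to an unnamed group |
| SAP 4.4, sample size, Cohort 1 | Size chosen for feedback on the first manual |
| SAP 4.4, sample size, Cohort 2 | Size chosen for the acceptability estimate, through its own 12 completers |

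Three of the four entries point to Cohort 2 and the fourth is silent. None says the cohorts are combined. Pooling would also make the Cohort 2 justification pointless, because the relevant number would then be 21 rather than 16.

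**What pooling would do if it happened.** Write m1 and m2 for the cohort means. The pooled mean is (5·m1 + 16·m2)/21, so Cohort 1 carries 5/21 = 24% of the weight.

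- Pooled passes while Cohort 2 fails when m1 − 28 ≥ (16/5)(28 − m2) = 3.2(28 − m2). Since m1 cannot exceed 32, this needs m2 ≥ 28 − 4/3.2 = 26.75.
- Example: m1 = 31 and m2 = 27.5 give (155 + 440)/21 = 28.3, a pass where Cohort 2 alone fails.
- Example: m1 = 26 and m2 = 28.5 give (130 + 456)/21 = 27.9, a fail where Cohort 2 alone passes.

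**How often the two readings would disagree, given pooling.** Treat the means as normal and ignore the ceiling at 32. The correlation of the pooled mean with the Cohort 2 mean is √(n2/(n1 + n2)). When both true means are 28, the chance of disagreement is arccos(correlation)/π, whatever the SD:

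- 5 + 16: correlation √(16/21) = 0.873, chance 16.2%.
- 4 + 12 (about 25% attrition in both cohorts): √(12/16) = 0.866, chance 16.7%.
- 5 + 12 (25% attrition in Cohort 2, none in Cohort 1): √(12/17) = 0.840, chance 18.2%.

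For other true means, over the assumed SD range:

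| True means (Cohort 1, Cohort 2) | 5 + 16 | 4 + 12 | 5 + 12 |
|---|---|---|---|
| 29, 29 | 2–11% | not computed | 3–14% |
| 30, 30 | at most 4% | not computed | at most 6% |
| 26, 29 | 21–24% | 21–27% | 25–36% |

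The largest figures need both an invented three-point gap between cohorts and attrition confined to Cohort 2.

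**What these figures measure.** The chance of a wrong verdict is the chance that someone pools, multiplied by the chance of disagreement given pooling. The calculation supplies only the second factor. The documents argue against the first.

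**The case for a change.** The strongest case is that the SAP is the document an analyst executes, and its rule for a primary outcome omits the analysis set. A sample size paragraph shows intent but does not define who enters a mean. An open set could also be chosen after the scores are seen, and naming the cohort would cost a few words.

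Part of this stands. The omission is real, the Cohort 1 scores should exist, and the arithmetic on pooling is correct. Copying the qualifier into the SAP would be harmless tidying.

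The rest does not carry. The protocol is part of the plan and states the population for this exact rule. A team that pooled would be departing from a written criterion, and any reader could see it, so the choice is not open after the data arrive. Nor is there anything to gain from asking that the interval be reported beside the verdict. The SAP already commits to 95% intervals for continuous variables, so a reader can see directly whether the interval covers 28. Its expected half-width follows from the sample size: t(0.975, 15)/√16 = 0.53 SD for 16 participants, and t(0.975, 11)/√12 = 0.64 SD for 12.

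**Conclusion.** No change is needed. The SAP sentence drops a qualifier that the protocol supplies and that the SAP's sample size section supports, so the intended analysis can be recovered without judgement: the Cohort 2 mean, set against 28, with its 95% interval. Followed together, the two documents give one verdict.

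A different verdict would require reading one SAP sentence in isolation, pooling two manual versions, and having a Cohort 2 mean near the threshold. Given pooling, disagreement is about 16% when both true means are 28 (5 + 16 or 4 + 12) and at most 4% when both are 30 (5 + 16). These figures rest on a normal model that ignores the scale ceiling and, away from 28, on an assumed SD of 2 to 5. Part of the SAP was not available for review. The conclusion does not depend on it, because the available text already settles the reading.

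### Does the full-scale trial decision ignore dropout because completion has no cutoff and the 75% adherence rule leaves its unit and cohort unstated?

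*SAP*

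**What the plan says.** SAP section 4.4, under the feasibility heading, names the components. Adherence is "intervention adherence (the number of treatment sessions successfully completed"), and it is adequate if "participants complete at least 75% of weekly treatment sessions within a 12-week period". Completion is "the percentage of enrolled participants who complete the follow-up assessment". For everything except adherence the SAP states: "We will not pre-determine cutoffs for other measures of intervention feasibility (recruitment, participation, and completion rate"). The sentence then goes on to say that these measures will be weighed carefully when the protocol is modified and the next phase is designed. An example compares recruitment and participation with the sample size that an efficacy trial would need.

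The same section says of the CSQ-8: "Participants will be given these questions at the end of follow-up assessment with an independent assessor". For the secondary measures, "we will calculate pre- to post-treatment changes by calculating standard effect sizes". The decision on a full-scale trial "will be based on whether ACT for Aphasia meets our criteria for feasibility and acceptability (Aim 2a") and on whether the functional results look promising, for which no threshold is given. The sample size paragraph says that "even with an overly conservative attrition rate of 25%, final completion rates would still be N=12".

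The Protocol sets the intervention at 10 sessions (Intervention description) and ties the CSQ-8 benchmark of 28 to the second cohort (Aim 2). It adds no adherence cutoff.

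**The concern.** Two kinds of loss could escape the decision.

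The first is loss to follow-up. Someone who attends the sessions and then misses the follow-up assessment gives no CSQ-8 score and no pre-post change. That person lowers the completion rate, which has no cutoff, and lowers neither of the two measures that have one. A pilot could lose many people this way and still meet both numerical criteria. The CSQ-8 mean would then describe only those who stayed, who may be the more satisfied.

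The second is stopping treatment early. Among the measures with a cutoff, only adherence registers this directly, and its wording allows several calculations. The 75% could be a group mean or a standard for each participant, people who stop could be counted or left out, and the base could be Cohort 2 or all 21. Feasibility is a primary outcome, so a result that depends on a choice made after attendance is known would be unwelcome.

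**Working it through.** **Inputs from the documents.** Cohort 1 has 5 participants and Cohort 2 has 16; there are 10 sessions; the cutoffs are 75% for adherence and 28 for the CSQ-8; assumed attrition is 25%. Attendance and CSQ-8 values below are assumptions.

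**The plan's own figure.** 16 × (1 − 0.25) = 12 completers. This reproduces. It supports precision and is not used as a pass mark.

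**Early stopping.** With n enrolled, k stopping after d sessions on average and the others averaging c, group-mean adherence over all enrolled is ((n − k)c + kd) / (10n). Take k = 4, which matches the plan's 25%, and c = 9.

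| Base | d | Calculation | Adherence |
|---|---|---|---|
| Cohort 2 | 0 | 108/160 | 67.5% |
| Cohort 2 | 2 | (12×9 + 4×2)/160 = 116/160 | 72.5% |
| Cohort 2 | 3 | 120/160 | 75.0% (break-even) |
| Cohort 2 | 4 | 124/160 | 77.5% |
| Both cohorts, no stoppers in Cohort 1 | 2 | (17×9 + 4×2)/210 = 161/210 | 76.7% |
| Cohort 2, stoppers left out | – | 108/120 | 90% |

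Read as a standard for each participant, 75% of 10 is 7.5, so 8 sessions. If every participant had to reach it, one early stopper would fail the rule.

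The crossing of 75% depends on c. If the other 12 attend all 10 sessions and 4 stop after 2, Cohort 2 adherence is (120 + 8)/160 = 80%. Even with no sessions attended by the 4, it is 120/160 = 75%, which still meets the cutoff. So with c = 10, the plan's own attrition figure cannot produce a failure on the group-mean reading, whether or not stoppers are counted.

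**Loss to follow-up alone.** If all 16 average 9 sessions and 8 then miss follow-up, adherence is 144/160 = 90% and completion is 8/16 = 50%. The loss lowers no measure that has a cutoff. This scenario uses twice the attrition that the SAP already calls overly conservative.

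**CSQ-8 with non-response.** If 12 respond with a mean of 29, the mean over all 16 falls below 28 when the other 4 would have averaged below (28×16 − 29×12)/4 = (448 − 348)/4 = 25.

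**What a completion cutoff would achieve.** For 12 of 16 (75%), the exact 95% interval is 47.6% to 92.7%. With a bar at 12 of 16, the binomial probability of missing it is 0.202 when true completion is 80%, and the probability of meeting it is 0.167 when true completion is 60%.

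**What the text already settles.** The session base is given: weekly sessions in a 10-session programme, within 12 weeks. The adherence sentence speaks of participants without limiting them to those who finish, and the paragraph treats completion as a separate measure. Sessions can be counted for anyone who starts. Nothing in the text supports the 90% calculation that drops stoppers.

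**The case for a change.** The strongest case for a change is that adherence is the only feasibility measure with a pass mark, and its definition should not be open once the data are in. Completion is defined over enrolled participants and the CSQ-8 benchmark is tied to Cohort 2, yet adherence is given neither base. Choosing Cohort 2 or both cohorts moves the result from 72.5% to 76.7% on plausible attendance. Completion, moreover, is promised attention for next-phase design, whereas the decision paragraph speaks of meeting criteria, and completion has none to meet. A change of wording would cost almost nothing.

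Part of this stands. The available text does not state the unit or the cohort for the 75% rule, and the two bases can fall on opposite sides of it. The CSQ-8 mean will also describe responders only.

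The rest carries less weight. The feasibility paragraph lists completion among the measures by which feasibility is assessed, and the decision paragraph does not restrict its criteria to numerical ones, so poor retention can count against a full-scale trial. The decision also involves an unthresholded judgement about functional outcomes, with 95% intervals that would tend to widen as people are lost. Someone who stops treatment but attends follow-up still contributes to the CSQ-8 mean and the effect sizes. The SAP is also supplied in part, and the 75% rule cites a source not available here, so a definition elsewhere cannot be ruled out.

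**Conclusion.** No change to the plan follows. Having no completion cutoff is a disclosed and fair trade-off. Completion will be reported over enrolled participants, the SAP promises 95% intervals for its outcomes, and the same sentence commits to using completion in planning. At 16 people a numerical bar would give the wrong signal about one time in five or six under the true rates shown. Adding a statement that retention is not a pass/fail criterion would alter no result.

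The adherence rule is a definition left partly unwritten. The ordinary reading counts every participant, including those who stop. Because the manual is revised between cohorts, an analyst would naturally show Cohort 2 separately, give the share of people at 8 or more sessions beside the mean, and state how many of those enrolled answered the CSQ-8. A gap of 76.7 − 72.5 = 4.2 percentage points across the cutoff would be read as borderline adherence under either base.

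This conclusion rests on the decision remaining a judgement informed by the criteria, as the SAP describes, and on the assumed attendance above. If the 75% rule were to decide the next trial mechanically, the unstated unit and cohort would matter more.
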